2.3 Risk/Benefit Assessment

2.3.1 Risk Assessment

Preclinical and clinical safety data, including adverse events (AEs) of interest, support the safety of 50 mg mirabegron in the treatment of patients with OAB.

The global OAB 12-week phase 2/3 studies (178-CL-046, 178-CL-047 and 178-CL-074) included 4414 patients treated with mirabegron, 2142 patients treated with placebo and 958 patients treated with tolterodine.

One or more serious adverse events (SAEs) were reported by 1.7% of mirabegron patients, 1.8% of placebo patients and 1.7% of tolterodine patients, with no apparent mirabegron dose response. The most common SAEs in the total mirabegron group were atrial fibrillation (mirabegron: 0.1%; placebo: < 0.1%; tolterodine: 0%), chest pain (mirabegron: 0.1%; placebo: < 0.1%; tolterodine: 0%) and pneumonia (mirabegron: 0.1%; placebo: < 0.1%; tolterodine: 0%) and pneumonia (mirabegron: 0.1%; placebo: < 0.1%; tolterodine: 0%). The most common treatment-emergent adverse events (TEAEs) (by preferred term) reported in the total mirabegron group were nasopharyngitis (mirabegron: 6.7%; placebo: 6.6%; tolterodine: 5.9%), hypertension (mirabegron: 5.0%; placebo: 5.0%; tolterodine: 4.5%) and blood glucose increased (mirabegron: 4.7%; placebo: 5.4%; tolterodine: 7.6%).

Study 178-CL-090 included 366 patients treated with mirabegron, 371 patients treated with tolterodine and 366 patients treated with placebo. One or more SAEs were reported by 1.4% of mirabegron patients, 1.6% of tolterodine patients and 1.9% of placebo patients. All SAEs were unique to a single patient in each treatment group. All SAEs were considered by the investigator to be not related to the IP except for headache and vomiting, which occurred in 1 patient in the tolterodine sustained release 4 mg group.

In the 1-year long term study, Study 178-CL-049, 1632 patients treated with mirabegron and 812 patients treated with tolterodine were included. The most common SAEs in the total mirabegron group were osteoarthritis (mirabegron: 0.2%; tolterodine: 0.1%) and cerebrovascular accident (mirabegron: 0.2%; tolterodine: 0.1%). The most common TEAEs (by preferred term) reported in the total mirabegron group were hypertension (mirabegron: 9.5%; tolterodine: 9.6%), urinary tract infection (UTI) (mirabegron: 5.7%; tolterodine: 6.4%) and nasopharyngitis (mirabegron: 4.1%; tolterodine: 3.1%).

AEs of interest have been thoroughly evaluated in all completed studies and do not represent product-related safety concerns. Potential risks included QT prolongation with supratherapeutic doses or in high-risk populations, increased heart rate with supratherapeutic doses, increased blood pressure with supratherapeutic doses, nonimmediate cutaneous hypersensitivity reactions and exposure in utero. The potential risks of QT prolongation, increased heart rate or increased blood pressure are greater with increasing exposure at supratherapeutic doses and can be mitigated with optimal dose selection.

Detailed reference safety information (RSI) can be found in the Investigator's Brochure.

2.3.2 **Benefit Assessment**

Although OAB is not a life-threatening disease, it has profound psychological and social influences on patients, their families and their caregivers, and may lead to a decline in quality of life.

Mirabegron is a highly selective β 3-AR agonist that activates β 3-ARs in the detrusor muscle of the bladder, resulting in muscle relaxation and an increase in bladder capacity, thereby improving OAB symptoms of urinary urgency, frequency and urge urinary incontinence. Mirabegron has a more favorable safety profile than antimuscarinic agents, which are often associated with dry mouth, constipation and blurred vision.

Medical evaluations/assessments associated with study procedures include; completion of electronic diary (e-diary), clinical laboratory tests, vital signs, physical examination, electrocardiogram (ECG), post void residual (PVR) volume assessments, and OAB Symptom Score (OABSS).

2.3.3 **Overall Risk-Benefit Conclusion**

Subjects participating in this study might benefit from administration of mirabegron. In addition, subjects might experience AEs related to mirabegron or procedural complications (e.g., blood draws, slight skin irritation from the adhesive on the ECG electrodes).

Overall, the risk associated with the participation of OAB patients in this study is considered acceptable.

3 **OBJECTIVES, ENDPOINTS AND ESTIMANDS**

Objectives and Endpoints:

The primary and secondary objectives and endpoints for this study are listed in the table below.

Table 2 Study Objectives and Enupoints				
Objectives Primary	Endpoints			
• To evaluate the efficacy of mirabegron 50 m for the treatment of OAB in Chinese subject	e e			
Secondary				
• To evaluate the safety of mirabegron for the treatment of OAB in Chinese subjects	• Incidence and severity of AEs.			
	• Clinical laboratory tests (hematology,			
	biochemistry and urinalysis)			
	• Vital signs (blood pressure and pulse)			
	• Routine 12-lead ECG			
22 Mar 2021	Astellas Page 18 of 68			

Table 2	Study Objectives an	nd Endpoints

Objectives

Endpoints

- Post Void Residual (PVR)
- To evaluate other efficacy variables of mirabegron 50 mg for the treatment of OAB

To explore mirabegron starting dose of 25 mg

- Change from baseline to the end of 12-week treatment period in mean number of grade 3 or 4 (PPIUS) urgency episodes, incontinence episodes, urge incontinence episodes/24 hours and OABSS
- All efficacy variables change from baseline to weeks 4 and 8
- Change from baseline to weeks 4, 8, and 12 in mean number of micturition/24 hours, mean number of grade 3 or 4 (PPIUS) urgency episodes, incontinence episodes, urge incontinence episodes/24 hours and OABSS

AE: adverse event; NA: Not applicable; OAB: overactive bladder; PPIUS: patient perception of intensity of urgency scale; OABSS: OAB Symptom Score.

Estimands

The estimand of most clinical importance for this study is defined by the following 4 attributes:

- Target population: all subjects who took at least 1 dose of the study drug, and in whom a non-missing measurement for mean number of micturitions per 24 hours at baseline and after administration of the study drug is available
- Outcome measurement: mean number of micturitions per 24 hours prior to switching (if switching occurs)
- Intercurrent events:
 - \circ Dose escalation
- Population-based summary: change from baseline to week 12/end of treatment (EoT) in micturition frequency per day within dose groups

For this study, the treatment estimand is considered appropriate because of the fact that the response of subjects prior to switching is of primary interest i.e., the estimate for 50 mg of mirabegron should be estimated from subjects who were randomized to 50 mg and the estimate for 25 mg should be estimated from subjects who were randomized to 25 mg while they were treated with 25 mg.

4 STUDY DESIGN AND DOSE RATIONALE

4.1 **Overall Study Design**

The study follows an open-label, randomized, 12-week, prospective, interventional postauthorization design for the treatment of OAB in approximately 249 Chinese subjects. Each subject will participate in one 12-week treatment period.

Planned total number of study sites include approximately 10-15 study sites across China.

This study is designed to support the IDL renewal and mirabegron safety surveillance in China. Subjects fulfilling the screening inclusion/exclusion criteria will be randomized in 2:1 ratio to 50 mg mirabegron and 25 mg mirabegron using a computer-generated randomization to reduce selection bias.

Treatments will be administered once daily orally recommended at the same time after meal during a 12-week, open-label treatment period. Study visits will take place at weeks 4, 8 and 12. For 25 mg mirabegron group, a dose escalation to 50 mg is permitted on visit 3 and visit 4 according to investigators' discretion.

4.2 Scientific Rationale for Study Design

An open-label design will be applied considering the primary objective is to assess the efficacy of mirabegron in Chinese population, measured with the mean number of micturition/24 hours. Subjects will be randomized to treatment to reduce selection bias. The ratio of 2:1 was determined based on the optimal dose of 50 mg rather than 25 mg. A follow-up of 12-week was chosen as previously documented in several Phase III clinical studies.

4.3 Dose Rationale

In mirabegron approval letter, NMPA has asked further investigation on the usage and dosage of (including the initiation dose) mirabegron in Chinese subjects and data should be submitted upon IDL renewal.

In accordance with Decree No. 81 of the Ministry of Health Provisions for Adverse Drug Reaction Reporting and Monitoring (July 2011) and draft guidance issues in 2013, drug manufacturers shall conduct regular safety surveillance for produced drugs and perform intensive monitoring over drugs during the new drug observation period as well as drugs imported for the first time within 5 years. Mirabegron sustained release tablets 50 mg and 25 mg are applicable for implementing the intensive monitoring.

In accordance with the NMPA's request, to continue the study on the posology of Chinese subjects, including the initial dose and taking drug after the meal and submit the study results upon renewal, both 25 and 50 mg doses of mirabegron will be investigated.

Mirabegron label in China recommended the use of 25mg in liver and renal impairment patients. However there is a risk that there will be absent or too few subjects in 25mg arm to make meaningful conclusions should the label is followed. Therefore the study recruits the same inclusion criteria to be randomized in both arms.

The 50mg group serves as the primary efficacy and safety assessment whilst the 25mg group is an exploratory starting dose observation in Chinese subjects. The investigators in 25mg group may want to assess in the next follow-ups if a dose escalation to 50mg is required at their own discretion. The study does not allow dose reduction from 50mg to 25mg as the former is considered a safe and effective recommended dose.

4.4 End of Study Definition

The end of the study is defined as the last visit or scheduled procedure shown in the Schedule of Assessments [Table 1] for the last subject in the study.

5 STUDY POPULATION

The study population will consist of Chinese male and female subjects with OAB (\geq 18 years of age). Eligible subjects must be able to provide written informed consent and meet all the inclusion criteria and none of the exclusion criteria.

All screening assessments must be completed and reviewed to confirm the potential subject meets all eligibility criteria. Prospective approval of protocol deviations to eligibility criteria (also known as protocol waivers or exemptions) is not permitted.

5.1 Inclusion Criteria

Subject is eligible for participation in the study if all of the following apply:

- 1. Institutional Review Board (IRB)/Independent Ethics Committee (IEC) approved written informed consent and privacy language as per national regulations must be obtained from the subject prior to any study-related procedures (including withdrawal of prohibited medication, if applicable).
- 2. Subject is considered an adult (\geq 18 years of age) according to local regulation at the time of signing the informed consent form (ICF).
- 3. Subject should exhibit symptoms of OAB for at least 12 weeks before initiation of the screening period.
- 4. Subject should have an average of ≥ 8 micturitions/24 hours.
- 5. Subject should have an average of ≥ 1 episode of grade 3 or 4 (PPIUS) urgency or urgency incontinence/24 hours, during a 3-day micturition diary period.
- 6. Female subject is not pregnant (see [Section 10.2 Appendix 2: Contraception Requirements]) and at least one of the following conditions apply:
 - a. Not a woman of childbearing potential (WOCBP) (see [Section 10.2 Appendix 2: Contraception Requirements])
 - b. WOCBP who agrees to follow the contraceptive guidance (see [Section 10.2 Appendix 2: Contraception Requirements]) from the time of informed consent through at least 30 days after final IP administration.
- 7. Female subject must agree not to breastfeed starting at screening and throughout the study period and for 30 days after final IP administration.
- 8. Female subject must not donate ova starting at first dose of IP and throughout the study period and for 30 days after final IP administration.
- 9. Male subject with female partner(s) of childbearing potential (including breastfeeding partner) must agree to use contraception (see [Section 10.2 Appendix 2 Contraception Requirements]) throughout the treatment period and 30 days after final IP administration.
- 10. Male subject must not donate sperm during the treatment period and for 30 days after final IP administration.

- 11. Male subject with pregnant partner(s) must agree to remain abstinent or use a condom for the duration of the pregnancy throughout the study period and for 30 days after final IP administration.
- 12. Subject agrees not to participate in another interventional study while participating in the present study, defined as 28 days prior screening until completion of the last study visit.

5.2 Exclusion Criteria

Subject will be excluded from participation in the study if any of the following apply:

Exclusion at Visit 1/Week -1 to -2 (Screening)

- 1. Subject has stress urinary incontinence as a predominant symptom.
- 2. Subject has an average total daily urine volume > 3000 mL (as recorded in a 3-day voiding diary period).
- 3. Subject has indwelling catheter or practices intermittent self-catheterization.
- 4. Subject has neurogenic detrusor overactivity or indicated pathology other than OAB.
- 5. Subject has monosymptomatic enuresis.
- 6. Subject has PVR volume of ≥ 100 mL or a clinically significant lower urinary tract obstructive disease, except if successfully treated.
- 7. Subject has anatomical anomalies (surgically treated or untreated) that affect lower urinary tract function.
- 8. Subject with hematuria on dipstick test. In the case of hematuria on dipstick test in a female during menstruation, the test can be repeated before randomization (after the end of menstruation).
- 9. Subject has lower urinary tract stones or clinically significant kidney stones requiring treatment.
- 10. Subject has interstitial cystitis.
- 11. Subject has suffered from chronic UTI or has had more than 3 UTIs in the 2 months prior to visit 1/week -1 to -2 (screening).
- 12. Subject has uncontrolled hypertension (sitting systolic blood pressure $[SBP] \ge 180 \text{ mmHg}$ or diastolic blood pressure $[DBP] \ge 110 \text{ mmHg}$).
- 13. Subject has pulse rate ≥ 110 beats per minute (bpm) or < 50 bpm.
- Subject has corrected QT interval by Fredericia (QTcF) > 440 msec on screening ECG or a risk of QT prolongation (e.g., hypokalemia, long QT syndrome [LQTS] or family history of LQTS or exercise-induced syncope).
- 15. Subject's aspartate aminotransferase (AST) or alanine aminotransferase (ALT) is
 ≥ 2 × upper limit of normal (ULN) or total bilirubin (TBL) is ≥ 1.5 × ULN according to
 age and sex (subjects with Gilbert's syndrome are excepted from the bilirubin threshold).
- 16. Subject has moderate or severe renal impairment.
- 17. Subject has a symptomatic (symptoms can include pain, fever, hematuria, new onset foul-smelling urine) UTI. Note: if the UTI is treated successfully (clinical recovery: confirmed by dipstick test and repeated dipstick test after 14 days [both should be negative]), the subject can be rescreened.

- 18. Subject has a history or presence of any malignancy (previous or current diagnosis of bladder or prostate cancer).
- 19. Subject uses any drugs that are sensitive cytochrome P450 2D6 (CYP2D6) substrates with a narrow therapeutic index or sensitive P-glycoprotein (P-gp) substrates after the start of washout.
- 20. Subject is using or has used prohibited prior and/or concomitant medication(s)
 [Section 10.5 Appendix 5 List of Excluded Concomitant Medications]. In case α1-AR antagonists, 5α-reductase inhibitors (5-ARIs) and Phosphodiesterase type 5 inhibitors (PED-Is) are used for Benign Prostatic Hyperplasia(BPH), Subject can be included in the study.
- 21. Subject has known or suspected hypersensitivity to mirabegron or any components of the formulations used.
- 22. Subjects previously treated for OAB including medication and nondrug treatment. If the treatment stopped for 2 weeks or more prior to the screening visit, Subjects can be included in the study.
- 23. Subject has participated in another clinical study (and/or subject has received any investigational therapy within 30 days (or 5 half-lives of the drug, or the limit set by national law, whichever is longer) prior to visit 1/week -1 to -2 (screening).
- 24. Subject has constipation as defined by the Rome IV criteria that cannot be successfully treated prior to study entry.
- 25. Female subject who has been pregnant within 6 months prior to screening or breastfeeding within 3 months prior to screening.
- 26. Subject has a positive serology test for hepatitis A virus (HAV) antibodies (immunoglobulin M [IgM]), hepatitis B core (HBc) antibodies, hepatitis B surface antigen (HBsAg), hepatitis C virus (HCV) antibodies, antibodies to human immunodeficiency virus (HIV) or syphilis at screening.
- 27. Subject is an employee of Astellas, the study-related contract research organizations (CROs) or the clinical unit.
- 28. Subject has any condition, which in the opinion of the investigator, makes the subject unsuitable for study participation.

Additional Exclusion at Visit 2/Week 0 (Baseline)

- 29. Subject has stress urinary incontinence as a predominant symptom.
- 30. Subject has an average total daily urine volume > 3000 mL (as recorded in a 3-day voiding diary period).
- 31. Subject has monosymptomatic enuresis confirmed by the bladder e-diary.
- 32. Subject suffers from a symptomatic (symptoms can include pain, fever, hematuria, new onset foul-smelling urine) UTI. Note: if a symptomatic UTI is present, all visit 2/week 0 (baseline) assessments must be postponed until the UTI is successfully treated (clinical recovery: confirmed by dipstick test and repeated dipstick test after 14 days [both should be negative]). The postponed visit 2/week 0 (baseline) should be within 14 days of the intended visit 2/week 0 (baseline).

- 33. Subject with hematuria on dipstick test. In the case of hematuria on dipstick test in a female during menstruation, the test can be repeated before randomization (after the end of menstruation).
- 34. Subject has uncontrolled hypertension (sitting SBP $\ge 180 \text{ mmHg}$ or DBP $\ge 110 \text{ mmHg}$).
- 35. Any reason, in the opinion of the investigator, that makes the subject unsuitable for study participation.

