- Submit results for any additional testing and possible etiology on the LA-CRF or an appropriate document.

Study Treatment Discontinuation

In the absence of an explanation for increased liver function tests, such as viral hepatitis, preexisting or acute liver disease, or exposure to other agents associated with liver injury, the subject may be discontinued from study treatment. The investigator may determine that it is not in the subject's best interest to continue study treatment. Discontinuation of study treatment should be considered if:

- ALT or AST $> 8 \times ULN$
- ALT or AST > $5 \times$ ULN for more than 2 weeks
- ALT or AST > 3 × ULN and† TBL > 2 × ULN or INR > 1.5) (if INR testing is applicable/evaluated)
- ALT or AST > $5 \times$ ULN and \dagger (TBL > $2 \times$ ULN in subjects with liver metastases)
- ALT or $AST > 3 \times ULN$ with the appearance of fatigue, nausea, vomiting, right upper quadrant pain or tenderness, fever, rash and/or eosinophilia (> 5%)

[†]Samples taken simultaneously or within a maximum of 24 hours.

In addition, if close monitoring for a subject with moderate or severe hepatic laboratory tests is not possible, study treatment should be discontinued.

Hy's Law definition: Drug-induced jaundice caused by hepatocellular injury, without a significant obstructive component, has a high rate of bad outcomes, from 10% to 50% mortality (or transplant).

The 2 "requirements" for Hy's Law are:

1. Evidence that a drug can cause hepatocellular-type injury, generally shown by an increase in AT elevations > 3 × ULN ("2 × ULN elevations are too common in treated and untreated subjects to be discriminating").

2. Cases of increased total bilirubin (at least 2 × ULN) with concurrent AT elevations at least 3 × ULN and no evidence of intra- or extra-hepatic bilirubin obstruction (elevated ALP) or Gilbert's syndrome [Temple, 2006].

FDA Guidance for Industry titled, "Drug-induced Liver Injury: Premarketing Clinical Evaluation" issued by the FDA on July 2009:

- 1. The drug causes hepatocellular injury, generally shown by a higher incidence of 3-fold or greater elevations above the ULN of ALT or AST than the (nonhepatotoxic) control drug or placebo.
- Among subjects showing such AT elevations, often with ATs much greater than 3 × ULN, one or more also show elevation of serum TBL to > 2 × ULN, without initial findings of cholestasis (elevated serum ALP).

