#### 6.5.2.1 Liver Safety Assessment

The liver safety assessments will be summarized by the categories below based on the measurements from Alkaline Phosphatase (ALP), Alanine Transaminase (ALT), total bilirubin, Aspartate Transaminase (AST) and their combination. These parameters will be based on measurements from the local laboratory.

The subject's highest value during the investigational period will be used.

- ALT >3xULN, >5xULN, >8xULN, >10xULN, >20xULN
- AST >3xULN, >5xULN, >8xULN, >10xULN, >20xULN
- ALT or AST >3xULN, >5xULN, >10xULN, >20xULN
- ALP > 1.5 xULN
- Total Bilirubin >2xULN
- (ALT or AST >3xULN) and (Total Bilirubin >2xULN or INR > 1.5)
- (ALT or AST >3xULN) and ALP <2xULN and Total Bilirubin >2xULN

Note: ALT, AST, ALP and Total Bilirubin results will be classified using the reference ranges supplied by the local laboratories.

The last 2 criteria where 2 or more parameters are evaluated will be with the measurements on the same day or up to 1 day apart (Samples to be taken simultaneously or within a maximum of 24 hours).

The denominator for each criterion will be the number of subjects who have at least one value during the investigational period. The number and percentage of subjects meeting the criteria during the investigational period will be summarized by treatment group.

A scatter plot of Peak AST or ALT data vs. Peak Total Bilirubin data will be presented for mirabegron subjects. Data will be presented as fractions of the ULN (of the local laboratories). In this scatter plot the area for Hy's Law will be presented, where ALT or AST >3xULN and Total bilirubin

>2xULN (ALT, ALT and Total Bilirubin from same blood sample or within a maximum of 24 hours). The area for hyperbilirubinemia (ALT and AST <3xULN and Total bilirubin >2xULN), Temple's corollary (ALT or AST >3xULN and Total bilirubin < 2xULN) will also be presented in this scatter plot.

Laboratory data will be provided in listing format by site and subject for the SAF.

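### The SAP's bilirubin row and hyperbilirubinemia area ignore baseline, so a Gilbert's subject admitted above 2 x ULN counts as an on-treatment abnormality without any change

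*Protocol*

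**What the plan says.** **Entry.** Protocol 5.2, criterion 15, excludes ALT or AST at or above 2 x ULN and total bilirubin (TBL) at or above 1.5 x ULN, with one exemption: "subjects with Gilbert's syndrome are excepted from the bilirubin threshold". No alternative bilirubin limit is set for the exempted subjects. Criterion 28 adds only a general discretion: "Subject has any condition, which in the opinion of the investigator, makes the subject unsuitable for study participation".

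**Analysis.** Protocol Appendix 4 (10.4) leaves the end-of-study liver analysis to the SAP. SAP 6.5.2.1 compares each subject with fixed multiples of ULN: "The subject's highest value during the investigational period will be used". One row is "Total Bilirubin >2xULN". Two rows combine ALT or AST above 3 x ULN with bilirubin. The first accepts TBL above 2 x ULN or INR above 1.5; the second adds an alkaline phosphatase condition: "ALT or AST >3xULN) and ALP <2xULN and Total Bilirubin >2xULN". Each denominator is everyone with at least one value in the investigational period.

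**Plot.** "In this scatter plot the area for Hy's Law will be presented, where ALT or AST >3xULN and Total bilirubin" is above 2 x ULN. The hyperbilirubinemia area is ALT and AST below 3 x ULN with TBL above 2 x ULN. Temple's corollary is ALT or AST above 3 x ULN with TBL below 2 x ULN. Neither the table nor the plot mentions baseline or Gilbert's syndrome.

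**Hy's Law.** The two-part definition cited in Appendix 4 requires "no evidence of intra- or extra-hepatic bilirubin obstruction (elevated ALP) or Gilbert's syndrome".

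**The concern.** The eligibility rule lets in a group whose bilirubin may already exceed the SAP's threshold, while the SAP treats any value above that threshold as something found on treatment. For such a subject the liver table reports the condition that came in at screening.

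The study supports licence renewal and safety surveillance in China, and both arms receive mirabegron. No untreated rate is available for judging one or two bilirubin cases. Where few events are expected, a single pre-existing case is visible: one subject in a 25 mg arm of 83 is 1.2%. The SAP already handles this for the ECG, where 6.5.4 sets absolute QTc categories beside categories of change from baseline. The liver section has no such pairing.

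**Working it through.** The plan gives no expected count of liver abnormalities, so there is no figure of its own to reproduce. The denominators follow from Protocol 9.2 and the 2:1 allocation: 166 on 50 mg, 166 / 2 = 83 on 25 mg, 166 + 83 = 249.

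**Step 1. Who can be above 2 x ULN at baseline?** Under criterion 15 at screening, a subject without recognised Gilbert's syndrome must have TBL below 1.5 x ULN. A subject with it has no TBL limit. Both must have ALT and AST below 2 x ULN.

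**Step 2. Apply the SAP rules to illustrative subjects with Gilbert's syndrome** (values in multiples of ULN; alkaline phosphatase 0.8 in every case).

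| Screening and Week 12 TBL | On-study ALT | TBL > 2 row | Combined rows | Plot area |
|---|---|---|---|---|
| 2.5, unchanged | 1.9 | counted | neither | hyperbilirubinemia |
| 1.8, unchanged | 1.0 | not counted | neither | none |
| 2.5, unchanged | 3.5 (new) | counted | both | Hy's Law |

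- Row 1: nothing changed on drug, yet the subject is counted.
- Row 2: values between 1.5 and 2 x ULN do no harm, so the problem starts only above 2 x ULN.
- Row 3: ALT above 3 x ULN must be new, because entry required below 2 x ULN. If the unchanged bilirubin is set aside, this subject falls in Temple's corollary. The pre-existing bilirubin moves the point into the Hy's Law area.

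**Step 3. Do other planned outputs separate these cases?** The shift table in SAP 6.5.2 uses only low, normal and high. A subject at 2.3 x ULN throughout and one rising from 1.2 to 4 x ULN both go from high to high and are both classed as no change. The table cannot show which cases above 2 x ULN were there before treatment. The change-from-baseline summaries are at group level. The subject listings do hold the answer.

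**Step 4. How many?** Let g be the share of the 249 subjects who have recognised Gilbert's syndrome, enter above 2 x ULN and are still above it on treatment. The documents give no value, so g is an assumption. Expected count = 249 x g; chance of at least one = 1 - (1 - g)^249.

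| g (assumed) | Expected | Chance of at least one |
|---|---|---|
| 0 | 0 | 0 |
| 0.1% | 0.25 | 22% |
| 0.5% | 1.2 | 71% |
| 1% | 2.5 | 92% |
| 2% | 5.0 | 99% |

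One case is 1/83 = 1.2% of the 25 mg arm or 1/166 = 0.6% of the 50 mg arm.

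**The case against.** Five points can be made for the plan.

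- **The reach is narrow.** Both combined rows and the Hy's Law area need an aminotransferase value that no eligible subject has at screening. Unchanged values affect one row and one plot area, and the plot itself keeps that area apart from Hy's Law. This stands, apart from the third case in the working.
- **A plotted area is not a case definition.** A reader might infer that the SAP contradicts Appendix 4 by omitting the Gilbert's condition. The documents do not support that. Appendix 4 says that it does not set the end-of-study analysis, and potential Hy's Law cases are judged clinically after other causes are considered (Protocol 10.3.1.2). The SAP draws a numerical region and does not say that points inside it are confirmed cases. This stands.
- **The data are already planned.** Laboratory listings, medical history by preferred term and direct bilirubin are all provided. With scheduled tests only at screening and Week 12, a careful reader could trace each case. This stands, but it leaves the liver table and plot unclear when read alone.
- **Few subjects can be affected.** The exemption works only for recognised Gilbert's syndrome, and investigators may decline a subject under criterion 28. This stands, and it rules out applying a general prevalence to all 249 subjects.
- **Removing subjects could hide injury.** If subjects raised at baseline were dropped from the combined rows, real liver damage in a subject with Gilbert's syndrome would leave the main counts. This stands and shapes the remedy.

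**Conclusion.** The point holds in a limited form. An unchanged bilirubin above 2 x ULN in a subject admitted under the exemption is reported as an on-treatment abnormality in the bilirubin-only row and the hyperbilirubinemia area. It can also turn a new isolated ALT or AST rise above 3 x ULN into an apparent Hy's Law point.

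A reader might go further and infer that unchanged pre-treatment values fill the combined rows and the Hy's Law area, or that at least one such case is almost certain. The entry limit on ALT and AST rules out the first. The second depends wholly on the assumed g: from 22% at 0.1% to 99% at 2%, and nil if no such subject enrols. The likely count is zero to a few subjects.

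The effect is confined to descriptive safety outputs. No test, decision rule or primary efficacy result depends on it. It merits correction because a reader of the liver outputs has no placebo rate for comparison and the remedy needs no new data.

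**What to change.** In SAP 6.5.2.1:

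1. Keep every subject in every row. Split the TBL above 2 x ULN row and both combined rows by baseline TBL (at or below 2 x ULN, and above 2 x ULN), each part with its own denominator. The baseline defined in SAP 6.5.2 can be used.
2. In the scatter plot, give a separate symbol to subjects with Gilbert's syndrome or baseline TBL above 2 x ULN. Leave them in whichever area their values fall, including Hy's Law.
3. List these subjects individually with baseline and on-treatment total and direct bilirubin.

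The cost is SAP wording, a few table lines and one flag in the liver dataset.

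Separately, the sponsor should reconcile Appendix 4 with criterion 15. Appendix 4 asks for further testing when bilirubin increases to more than 2 x ULN, and it classes a confirmed value above that level, on its own, as a moderate abnormality. It makes no exception for Gilbert's syndrome, yet criterion 15 admits such subjects. Because the testing instruction speaks of an increase, it is unclear whether an unchanged value is meant to count. The passages should be made to agree; which rule is clinically right is for the sponsor to decide.
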